5.4.1 Rationale for dose

For adult subjects, the LCM 100mg/day dose was selected to be the starting dose for this study to ensure a safe and well-tolerated up-titration scheme. The LCM 400mg/day maintenance dose was well tolerated and demonstrated efficacy in 3 primary efficacy studies as adjunctive therapy in subjects with partial-onset seizures. In SP0961 (the Phase 2 pilot study) and SP0962 (the open-label extension study) in subjects with uncontrolled PGTC seizures with IGE, the 400mg/day dose was also well tolerated. Generally, the doses of AEDs used for the treatment of partial-onset seizures are similar to those used to treat generalized seizures. Thus, the 300mg/day to 400mg/day target dose range is considered the optimal maintenance dose for the population with uncontrolled PGTC seizures with IGE.

Based on the currently available LCM pediatric safety and PK data from SP847 and SP1047, as well as on information available in the medical literature, the pediatric dosing recommendations for SP0982 are to achieve LCM plasma concentrations similar to the average steady-state LCM plasma concentration reached after a LCM 400mg/day dose administration in adult studies.

A population PK model (CL0177) was developed using plasma concentration data and demographic information from all pediatric subjects in SP847 and SP1047. The data consisted of 402 LCM plasma concentration-time records obtained in 79 children, with a balanced distribution of 14, 22, 25, and 18 subjects in the age groups 6 months to <2 years, 2 to <6 years, 6 to <12 years, and 12 to <18 years, respectively. Body weights ranged from 6kg to 76kg.

Different pediatric dosing adaptation schemes were simulated with the aim of reaching the range of average steady-state plasma concentration ($C_{SS,ave}$) obtained in adults receiving LCM 400mg/day, which is approximately 8µg/mL (90% prediction interval: 5µg/mL to 12µg/mL). This was achieved with a dosing scheme of 12mg/kg/day in children weighing <30kg, 8mg/kg/day in children weighing from 30kg to <50kg, and 400mg/day in children weighing ≥50kg. The proportional pediatric dose adaptation corresponding to 300mg/day in adults and in children weighing ≥50kg, are 8mg/kg/day in children weighing <30kg, and 6mg/kg/day in children weighing from 30kg to <50kg.

5.4.2 Rationale for second PGTC seizure

The primary efficacy variable, the time to the second PGTC seizure, has several advantages from a clinical and methodological perspective. In traditional adjunctive study designs, the primary endpoint is percent reduction in seizure frequency over the entire Treatment Period; which requires a higher frequency of seizures at entry. Using the time to second seizure, the frequency of Baseline seizures and the duration of the Prospective Baseline can be reduced as the endpoint is time to reach an event (second seizure), rather than a percentage decrease in the number of events (seizures). This expands the patient population under study and allows for enrollment of subjects more representative of the broader PGTC seizure population. Furthermore, subjects are treated for up to 24 weeks in a traditional adjunctive design, depending upon the titration schedule of the active treatment. Subjects must remain on treatment as they continue to experience seizures. In the time to n^{th} seizure design, subjects are required to remain in the study for a minimum of 6 weeks. If a subject experiences ≥2 seizures while on treatment, then after 6 weeks the subject exits the study, rather than continuing to have PGTC seizures, while remaining eligible to receive LCM in the open-label extension study (EP0012).

The rationale for time to second seizure was established by using data from an adjunctive study in subjects with PGTC seizures, using an 8-week Baseline, 7-week Titration, and 12-week Maintenance Period comparing lamotrigine and placebo (French et al, 2007). This posthoc analysis using a Cox proportional hazards model revealed that time to third seizure was statistically significant with a hazard ratio of 0.533 (lamotrigine 48.2%, placebo 25.4%). Lamotrigine requires a long Titration Period, where a minimally effective dose is not reached until the fifth week of the Titration Period (100mg/day). Lacosamide, by comparison, reaches a minimally effective dose in the second week (200mg/day) for a majority of trial subjects. Since a majority of the events in the lamotrigine study occurred before Day 21, it is likely that fewer events would occur using LCM as it reaches an effective dose earlier; therefore, time to second seizure was chosen as a reasonable endpoint from a clinical and statistical perspective.

5.4.3 Rationale for minimum duration of treatment

The minimum duration of the Treatment Period for each subject will be 6 weeks. There are 3 reasons for the requirement of a minimum Treatment Period duration:

- To collect a minimum of placebo-controlled safety data for the entire study population
- To allow for the analysis of reduction in seizure days for non-PGTC seizures (eg, absence or myoclonic seizures)
- To allow for increased flexible dosing during titration

Primary generalized tonic-clonic seizures are sparse but severe clinical events that profoundly affect the lives of patients. Should the minimum duration of the study be longer (eg, 12 weeks), this would prolong the time subjects randomized to placebo (or subjects randomized to LCM who do not respond to the treatment) have to stay on a nonefficacious treatment. By allowing subjects to exit the study after completing 6 weeks of the Treatment Period, sufficient double-blind safety data can be collected from a high proportion of subjects to be meaningful. Moreover, additional safety data will be available from the open-label, long-term, extension study (EP0012).

5.4.4 Rationale for selected age range

Idiopathic generalized epilepsies are assumed to have a genetic etiology and onset almost always occurs during childhood or adolescence, although there are exceptions; some patients develop these kinds of epilepsies after the second decade of life or, rarely, even later.

There are a number of different epilepsy syndromes within the group of IGEs. Patients with the most common IGE syndromes (ie, childhood absence epilepsy, juvenile absence epilepsy, juvenile myoclonic epilepsy, and epilepsy with grand mal seizures on awakening) may experience generalized tonic-clonic seizures. Onset of these syndromes normally occurs during childhood and adolescence.

The ≥ 4 -year age cutoff was established based on the difficulty of establishing a clear diagnosis of IGE in younger subjects with PGTC seizures. This is further supported by epidemiology data, which indicates that the incidence and prevalence of generalized epilepsies is lower in preschoolers compared to older children (Olafsson et al, 2005).

6 SELECTION AND WITHDRAWAL OF SUBJECTS

6.1 Inclusion criteria

To be eligible to participate in this study, all of the following criteria must be met:

1. An Institutional Review Board (IRB)/Independent Ethics Committee (IEC) approved written Informed Consent/Assent form is signed and dated by the subject or by the parent(s) or legal representative. The Informed Consent form or a specific Assent form, where required, will be signed and dated by minors.
2. Subject/legal representative is considered reliable and capable of adhering to the protocol (eg, able to understand and complete diaries), visit schedule, and medication intake according to the judgment of the investigator.
3. Male and female subjects ≥ 4 years of age.
4. Subject with a confirmed diagnosis at least 24 weeks prior to Visit 1 and a disease onset prior to 30 years of age, consistent with IGE experiencing PGTC seizures (Type IIE) that are classifiable according to the ILAE Classification of Epileptic Seizures (ILAE, 1981).
5. Subject has ≥ 3 PGTC seizures during the 16-week Combined Baseline (12-week Historical Baseline plus 4-week Prospective Baseline) distributed as described below:
 - at least 3 PGTC seizures should have occurred during the 16-week Combined Baseline Period,

- at least 2 PGTC seizures should have occurred during the 12-week Historical Baseline Period,
- of the above seizures, at least 1 PGTC seizure should have occurred during the first 8 weeks and at least 1 PGTC seizure should have occurred during the second 8 weeks of the 16-week Combined Baseline Period.

The schematic diagram for the Combined Baseline Period eligibility is provided in [Figure 5-1](#). Examples of PGTC seizure frequency and eligibility are provided in the table below:

| Number of PGTC seizures | | | Is subject eligible? (In terms of Inclusion Criterion 5) |
|--|---------------------------------------|---|--|
| Historical Baseline Weeks -16 to -8 | Historical Baseline Weeks -8 to -4 | Prospective Baseline Weeks -4 to 0 (Visit 1 to Visit 2) | |
| 2 | 1 | 0 | Yes |
| 3 | 0 | 0 | No* |
| 1 | 1 | 1 | Yes |
| 0 | 2 | 1 | No |
| 1 | 2 | 0 | Yes |
| 2 | 0 | 1 | Yes |
| 1 | 0 | 2 | No |
| 1 | | 0 | No* |

Screening Visit

*Eligible to roll over to EP0012 if all other inclusion criteria are also met.

PGTC=primary generalized tonic-clonic

6. If a brain magnetic resonance imaging (MRI)/computed tomography (CT) scan has been performed, there must be no evidence of any progressive abnormality or any lesion likely to be associated with partial-onset seizures.
- 7a. Subject has been maintained on a stable dose regimen of 1 to 2 non-benzodiazepine marketed AEDs with no benzodiazepine AEDs **OR** 1 benzodiazepine marketed AED with 1 to 2 non-benzodiazepine marketed AEDs (see examples in the table below) for at least 28 days prior to Visit 1 with or without additional concurrent stable VNS (see Section 7.8).

Vagus nerve stimulation must have been in place for at least 6 months prior to Visit 1 with constant settings for at least 28 days prior to Visit 1 and during the Prospective Baseline and Treatment Period.

| Benzodiazepine AEDs | Non-Benzodiazepine AEDs | Total AEDs | Is subject eligible? (In terms of Inclusion Criterion 7) |
|---------------------|-------------------------|------------|--|
| 0 | 1 | 1 | Yes |
| 0 | 2 | 2 | Yes |
| 1 | 1 | 2 | Yes |
| 1 | 2 | 3 | Yes |
| 1 | 0 | 1 | No |
| 0 | 3 | 3 | No |
| 2 | 1 | 3 | No |

AED=antiepileptic drug

8. Subjects are required to have had an EEG report consistent with IGE (eg, generalized ≥ 3 Hz epileptiform discharges and a normal EEG background) confirmed by a Central Reviewer.

6.2 Exclusion criteria

Subjects are not permitted to enroll in the study if any of the following criteria is met:

1. Subject has previously been randomized in this study or subject has previously been assigned to treatment in a clinical study of LCM.
2. Subject has participated in another study of an investigational medicinal product (IMP) or an experimental medical device within the last 30 days or is currently participating in another study of an IMP or a medical device.
3. Subject has a history of partial-onset seizures or EEG findings indicative of partial-onset seizures.
- 4a. Subject has symptomatic generalized epilepsy ([ILAE, 1989] (eg, Lennox-Gastaut Syndrome typically presenting with seizures including tonic seizures), some other related syndrome like Doose's syndrome (typically presenting with myoclonic-atonic seizures), or evidence of both focal and generalized epilepsy.
5. Subject has a history of convulsive status epilepticus 1 year prior to screening.
6. Subject has a current or previous diagnosis of pseudoseizures, conversion disorders, or other nonepileptic ictal events which could be confused with seizures.
7. Subject has any medical or psychiatric condition that, in the opinion of the investigator, could jeopardize or would compromise the subject's ability to participate in this study.
8. Subject has a lifetime history of suicide attempt (including an actual attempt, interrupted attempt, or aborted attempt), or has suicidal ideation in the past 6 months as indicated by a positive response ("Yes") to either Question 4 or Question 5 of the Columbia-Suicide Severity Rating Scale (C-SSRS) at Screening.
9. Subject has a known hypersensitivity to any components of the investigational product(s).

-
10. Subject has a medical condition that could reasonably be expected to interfere with drug absorption, distribution, metabolism, or excretion.
 11. Subject has multiple drug allergies or severe drug allergy.
 12. Subject has any history of alcohol, opioid, or other drug use disorder, as per Diagnostic and Statistical Manual of Mental Disorders, Fifth Edition (DSM-V), within the previous 2 years.

Note: previous sporadic cannabis use is not exclusionary as long as subject is requested and agrees not to use cannabis during the study.
 13. Subject has an acute or sub-acutely progressive central nervous system disease.
 14. Subject with a known history of severe anaphylactic reaction or serious blood dyscrasias.
 15. At Visit 1, subject has $\geq 2x$ upper limit of normal (ULN) of any of the following: alanine aminotransferase (ALT), aspartate aminotransferase (AST), alkaline phosphatase (ALP), or $>ULN$ total bilirubin ($\geq 1.5xULN$ total bilirubin if known Gilbert's syndrome). If subject has elevations only in total bilirubin that are $>ULN$ and $<1.5xULN$, fractionate bilirubin to identify possible undiagnosed Gilbert's syndrome (ie, direct bilirubin $<35\%$).

For randomized subjects with a Baseline result $>ULN$ for ALT, AST, ALP, or total bilirubin, a Baseline diagnosis and/or the cause of any clinically meaningful elevation must be understood and recorded in the eCRF.

If subject has $>ULN$ ALT, AST, or ALP that does not meet the exclusion limit at screening, repeat the tests, if possible, prior to dosing to ensure there is no further ongoing clinically relevant increase. In case of a clinically relevant increase, inclusion of the subject must be discussed with the Medical Monitor.

Tests that result in ALT, AST, or ALP up to 25% above the exclusion limit may be repeated once for confirmation. This includes re-screening.
 16. Subject has impaired renal function (ie, creatinine clearance [CL_{Cr}] is $<30\text{mL}/\text{min}$) at Screening (see Section 10.2).
 17. Subject has a known cardiac channelopathy, such as Brugada syndrome.
 18. Subject has sick sinus syndrome without a pacemaker, or second- or third-degree atrioventricular (AV) block, or subject has any other clinically significant ECG abnormalities.
 19. Subject has experienced a myocardial infarction in the last 3 months prior to Visit 1.

20. Subject has New York Heart Association Class III or Class IV heart failure.

| New York Heart Association Criteria: | |
|---|--|
| Class I | Patients with cardiac disease, but without resulting limitations of physical activity. Ordinary physical activity does not cause undue fatigue, palpitation, dyspnea, or anginal pain. |
| Class II | Patients with cardiac disease resulting in slight limitation of physical activity. They are comfortable at rest. Ordinary physical activity results in fatigue, palpitation, dyspnea, or anginal pain. |
| Class III | Patients with cardiac disease resulting in marked limitation of physical activity. They are comfortable at rest. Less than ordinary activity causes fatigue, palpitation, dyspnea, or anginal pain. |
| Class IV | Patients with cardiac disease resulting in inability to carry on any physical activity without discomfort. Symptoms of heart failure or the anginal syndrome may be present even at rest. If any physical activity is undertaken, discomfort is increased. |

The Criteria Committee of the New York Heart Association, 1994

21. Female subject who is pregnant or nursing and/or a woman of childbearing potential who is not surgically sterile, 2 years postmenopausal, or does not practice 1 highly effective method of contraception (according to International Council for Harmonisation [ICH] guidance, defined as those that result in a failure rate of <1% per year when used consistently and correctly), unless sexually abstinent, for the duration of the study.

Female subject of childbearing potential taking enzyme-inducing antiepileptic drugs (EI-AEDs: carbamazepine, phenytoin, barbiturates, primidone, topiramate, oxcarbazepine) who is not surgically sterile, 2 years postmenopausal, or does not practice 1 highly effective method of contraception according to the World Health Organization recommendation (ie, depot medroxyprogesterone acetate, norethisterone enantate, intrauterine devices, combined injectables, and progestogen implants) with administration of EI-AEDs or does not practice 2 combined methods of contraception (ie, combined hormonal contraception plus barrier method with spermicidal agent), unless sexually abstinent, for the duration of the study.

22. Subject has been taking 1 or more of the following medications on a regular basis within 28 days prior to Visit 1: monoamine oxidase A (MAO-A) inhibitors, barbiturates (for indications other than epilepsy), or clozapine.

23. Subject has been treated with felbamate and has experienced any serious toxicity issues (defined as liver failure, aplastic anemia) with this treatment. Subjects treated with felbamate for <12 months are excluded. Subjects treated with felbamate for ≥12 months prior to Visit 1 and who have not experienced serious toxicity issues are eligible.

24. Subject has taken vigabatrin in the preceding 6 months. Note: A subject with a history of vigabatrin treatment must have had a visual perimetry test at least 6 months following conclusion of treatment. The results of the visual perimetry test must have shown either no damage or a visual field defect associated with 1 of the following 2 conditions: 1) there was no change from a visual field test done at some point while the subject was taking vigabatrin, or 2) there was no change from a visual field test done shortly after stopping vigabatrin administration.

25. Subject is on a ketogenic diet that has either changed within the 4 weeks prior to Visit 1 or is expected to change during the study.

Subjects may be rescreened with prior consultation and permission of the Medical Monitor. If the investigator has any doubts concerning the subject's eligibility, he/she should consult the UCB Study Physician or representative for clarification.

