7.8 Concomitant medication/treatment

7.8.1 Permitted concomitant treatments (medications and therapies)

Subject has been maintained on a stable dose regimen of 1 to 2 non-benzodiazepine marketed AEDs **OR** 2 to 3 AEDs (with 1 AED identified as a benzodiazepine) for at least 28 days prior to Visit 1 and during the Prospective Baseline and Treatment Period with or without additional concurrent stable VNS.

- Vagus nerve stimulation must have been in place for at least 6 months prior to Visit 1 with constant settings for at least 28 days prior to Visit 1 and must remain unchanged during the course of the study.
- The chronic (daily dose) use of a benzodiazepine is allowed regardless of indication and will be counted as 1 of the 3 allowed AEDs.
- Intermittent use of benzodiazepines (limited to 2 doses per 28 days) is allowed only for epilepsy indications if established at least 28 days prior to Visit 1. Intermittent use of benzodiazepines for any other indication is prohibited during the study.

Contraceptive treatment is allowed as described in in Section 6.2 (Exclusion Criterion 21). Recommended contraception methods for subjects on enzyme-inducing antiepileptic drugs (EI-AEDs) or not on EI-AEDs are detailed in Section 17.9.

Stable use of amphetamines and sedative antihistamines is allowed during the study.

Neuroleptics (except for clozapine) are allowed during the study but the investigator should make every effort to keep the dose stable.

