17.9 Contraception table

| Method | Abbreviation | no EI-AEDs | EI-AEDs |
|---------------------------------------|--------------|--------------|---------------------|
| combined injectable contraceptives | CIC | ok | ok |
| combined patch | P | ok | needs barrier |
| combined vaginal ring | R | ok | needs second method |
| low-dose combined oral contraceptives | COC | ok | needs barrier |
| etonogestrel implant | ETG | ok | ok |
| levonorgestrel implant | LNG | ok | ok |
| depot medroxyprogesterone acetate | DMPA | ok | ok |
| norethisterone enantate | NET-EN | ok | ok |
| progestogen-only pills | POP | ok | needs barrier |
| emergency contraceptive pills | ECP | NA | NA |
| copper-bearing intrauterine devices | CU-IUDs | ok | ok |
| levonorgestrel-releasing IUDs | LNG-IUDs | ok | ok |
| barrier methods | BARR | not eligible | not eligible |
| fertility awareness-based methods | FAB | not eligible | not eligible |
| lactational amenorrhoea method | LAM | not eligible | not eligible |
| coitus interruptus | CI | not eligible | not eligible |
| female and male sterilization | STER | ok | ok |

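### For women on enzyme-inducing AEDs, the recommended-contraception table in Section 17.9 accepts the progestogen-only pill with a barrier, which Exclusion Criterion 21 rejects

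*Protocol*

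**What the plan says.** Section 7.8.1 sets the order of authority. It first states: "Contraceptive treatment is allowed as described in in Section 6.2 (Exclusion Criterion 21)." It then adds: "Recommended contraception methods for subjects on enzyme-inducing antiepileptic drugs (EI-AEDs) or not on EI-AEDs are detailed in Section 17.9."

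The EI-AED paragraph of Criterion 21 (Section 6.2) applies to women of childbearing potential who are not surgically sterile, two years past menopause or abstinent. It recognises two routes:

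- **Single method.** The list is given in brackets: "ie, depot medroxyprogesterone acetate, norethisterone enantate, intrauterine devices, combined injectables, and progestogen implants".
- **Two methods together.** The criterion excludes a woman who "does not practice 2 combined methods of contraception (ie, combined hormonal contraception plus barrier method with spermicidal agent").

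Section 17.9 lists 17 methods, with one column for women not on EI-AEDs and one for women who are. Two rows matter most:

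- "progestogen-only pills | POP | ok | needs barrier"
- "low-dose combined oral contraceptives | COC | ok | needs barrier"

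The same table marks barrier-only, fertility-awareness, lactational and withdrawal methods as not eligible in both columns.

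**The concern.** The protocol gives sites two texts on one eligibility question, and they disagree for one method. The table has its own label for unacceptable methods and does not use it for the progestogen-only pill. An investigator would therefore read the entry as acceptable once a barrier is added. Criterion 21 gives no such permission.

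At stake is an avoidable eligibility deviation in a rule that protects against fetal exposure, in a study with up to 28 weeks of study drug (Section 5.1.1). The group is plausible: Section 2 names phenobarbital and topiramate among the drugs used in this population, and Criterion 21 counts barbiturates and topiramate as enzyme inducers.

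**Working it through.** No arithmetic applies beyond counting rows. The check sets the EI-AED column of Section 17.9 against the EI-AED paragraph of Criterion 21.

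| Section 17.9 method | Rows | EI-AED entry | Against Criterion 21 |
|---|---|---|---|
| Combined injectable, two implants, DMPA, NET-EN, two IUD types | 7 | ok | On the single-method list: agree |
| Combined patch, combined pill | 2 | needs barrier | Two-method route: compatible, though the table omits the spermicide |
| Combined ring | 1 | needs second method | Compatible if the second method is a spermicidal barrier |
| **Progestogen-only pill** | **1** | **needs barrier** | **On neither route: contradiction** |
| Emergency pill | 1 | NA | No conflict |
| Barrier alone, fertility awareness, lactational, withdrawal | 4 | not eligible | Agree |
| Sterilization | 1 | ok | Female sterilization is covered; male part depends on meaning |

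Total: 7 + 2 + 1 + 1 + 1 + 4 + 1 = 17 rows.

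**Progestogen-only pill plus barrier, step by step**

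1. *Single-method route.* The pill is not among the five methods listed (DMPA, NET-EN, IUDs, combined injectables, progestogen implants). Not met.
2. *Two-method route.* This needs a combined hormonal product. A progestogen-only pill is not one, and the table itself lists it apart from the combined oral contraceptives. Not met.
3. *Meaning of the 'or'.* If the routes are alternatives, which is evidently intended, 0 of 2 are met and the woman is excluded. If both are required, 0 of 2 are met and she is again excluded.
4. *Are the lists closed?* Both are introduced by 'ie'. The protocol uses 'eg' where it gives examples (Criterion 4a) and 'ie' where it defines (Criterion 16), so nothing supports reading Criterion 21 as open-ended.

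**Sterilization row.** The entry is "female and male sterilization | STER | ok | ok". It does not mention a partner. The trial enrols "Male and female subjects", so the male part may simply refer to subjects. If it means a sterilized partner of a female subject, that too is absent from the EI-AED paragraph. This is conditional, and the finding does not rest on it.

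**The case against.** The strongest reply is that the protocol already ranks the two texts. Section 7.8.1 names Criterion 21 first as the rule and only then points to the table, and eligibility is decided on the inclusion and exclusion criteria (Section 8.1.1). That limits the harm and indicates which text should yield. It does not remove the inconsistency, because the very next sentence recommends the table's methods for women on EI-AEDs.

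A second reply is that safeguards exist. Section 6.2 tells an investigator in doubt to consult the sponsor's study physician, a negative urine test is needed before the first dose (Table 5-1, footnote p), and a positive test requires withdrawal (Section 6.4). These are real but do not reconcile the rules: the first applies only when there is doubt, which the table may dispel, and the tests detect pregnancy rather than prevent it.

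Third, nothing in the protocol shows that a progestogen-only pill with a barrier protects less than a combined pill with a barrier. That is right, and no such claim is made here; the point is that one text accepts what the other excludes.

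Fourth, the amendment history leaves the sponsor's intention open. The EI-AED paragraph came in with Amendment 2, and the sentence pointing to the table with Amendment 4. The table might be the newer view. This stands as a reason to ask the sponsor, but as written Criterion 21 governs.

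**Conclusion.** The inconsistency holds and is minor. In the EI-AED column, 1 of 17 rows contradicts Criterion 21 under either reading of its 'or'; a second, the male part of the sterilization row, would do so only if it means a sterilized partner. The conclusion rests on taking 'ie' in its ordinary defining sense and on reading *needs barrier* as acceptance once a barrier is added, which the table's separate *not eligible* label supports.

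The consequence is a possible ineligible-subject deviation. It requires a woman of childbearing potential on an EI-AED who uses this particular method, and the protocol gives no basis for estimating how many there would be.

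**What to change.** In the EI-AED column of Section 17.9, change the progestogen-only pill entry to *not eligible*, so that the table matches the stricter, governing criterion. If the sponsor intends to accept this method, add the pill with a spermicidal barrier to the EI-AED paragraph of Criterion 21 instead.

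Two optional tidy-ups: state whom the male sterilization entry refers to and, if it means a partner, make the criterion and table agree; and mention the spermicidal agent in the patch, combined pill and ring rows. Those three rows are compatible with Criterion 21, so this is clarification only.

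The cost is one table cell, or one phrase of the criterion, and no new assessments. With the stricter choice a few women may have to change method or not enrol, which Criterion 21 already requires.
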